 limited information concerning associations with PFAS exposures and most cancers and other adult
 diseases (ATSDR 2017a).

Epidemiologic studies of subjects exposed to PFOA and PFOS at background levels and at occupational settings have reported positive associations with number of health outcomes and conditions. Lipid and cholesterol concentrations were associated with increased PFOA or PFOS (Frisbee 2010; Nelson 2010; Fletcher 2011; Steenland 2015), as were increased uric acid levels (Costa et al., 2009; Steenland 2010; Shankar 2011; Geiger 2013; Gleason 2015), concentrations of thyroid and sex hormones (Olsen and Zobel 2007; Knox 2011; Jain 2013; Wen 2013; Winquist and Steenland 2014), immune parameters
 (Dalsager2016), and reproductive effects (Joensen 2013; Kristensen 2013; Crawford 2017).

Associations with liver enzymes were found with PFAS in most cross-sectional studies (Olsen 2000; Sakr2007; Lin 2010; Gallo 2012; Gleason 2015) but were weaker or found no association in the cohort studies of liver enzymes (Sakr 2007b, Darrow 2016). Structural protein cytokeratin 18 (CK-18) and its components have been used as a new non-invasive serum biomarker for non-alcoholic fatty liver disease and suspected steatohepatitis for adults and children (Fieldstein 2013, Shen 2012, Vos 2008). Prevalent coronary heart disease was positively associated in a cross sectional examination of NHANES (Shankar 2012) but not in cohort designs (Winquist 2014b; Mattsson 2015).

Two studies of osteoarthritis show association with PFOA in cross sectional analyses (Innes 2011, Uhl 2013) but no association in longitudinal analyses (C8 Science Panel 2012a). Another cross-sectional NHANES study (Khalil 2016) found an association with osteoporosis among women for PFHxS. Two NHANES studies (Lin 2014, Khalil 2016) also found associations with bone mineral density. Although, these studies are cross-sectional, they provide important evidence for a link between PFAS exposures and osteoarthritis and osteoporosis unless there is evidence that confounding or reverse causation can explain these results.

17 In evaluation of kidney function, data from Watkins (2013) and Dhingra (2017) showed that while 18 measured PFOA showed positive association, modeled PFOA concentrations had no relation to eGFR 19 illustrating example of potential reverse causality. C8 Science panel found no association with the 20 nonmalignant renal disease in their cohort study (2021b)

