function	C8 1.078 1-5 yrs	2.3% change (mean difference = 0.17 µg/dI)	levels were about 20 $\mu g/L$ SD for TT ₄ as	
114	3,132 6-10 yrs		estimated at 1.4.	
	6,447 >10 - 17 yrs		Percent change in	
			TT ₄ was converted to	
			mean difference	
			assuming the	
			median TT_4 was ref.	
Thyroid			Provalence-0.6%	>16 000/stratum
disease		(PFOS: OR < 1.0)	(used PEOA results)	210,000/stratum
Uric Acid	Kataria 2015,	PFOS: 4 th vs 1 st guartile =	Mean PFOS serum	556/stratum
	NHANES	+0.19 mg/dL	level = 12.8 μg/L. SD	,
	1,960; 12-18 yrs		= 1.19.	
Hyperuricemia	Geiger 2013,	PFOS: 4 th vs 1 st quartile,	Mean PFOS serum	400/stratum
	NHANES	OR=1.65	level =16.6.	
	1,772; 12-18 years		Prevalence=16%	
eGFR	Kataria 2015	PFOA mean serum level	Standard	275/stratum
	1,960; 12-18 yrs	=3.5 μg/L. mean	deviation=27.6	
		difference= -6.6		
Testosterone	Lopez-Espinosa 2016,	PFOS (IQR):	Percent change was	Boys: 404/stratum
	C8	-5.8% boys (diff=1.9)	converted to mean	Girls: 368/stratum
	1,169 boys; 6-9 yrs	-6.6% girls (diff=2.45)	difference assuming	
	1,123 girl; 6-9 yrs		median testosterone	
			level was ref. level.	
			SD estimated at	
			9 63 for hovs	
IGF-1 (Insulin-	Lopez-Espinosa 2016.	PFHxS (IQR):	Percent change was	146/stratum
like growth	C8	Boys: -2.5% (diff=17.3)	converted to mean	,
factor – 1)		Girls: -2.1%	difference assuming	
			median IGF-1 in boys	
			as ref. level. SD	
			estimated as 52.6	
Delayed	Lopez-Espinosa 2011.	PFOS: mean serum level	OR for delayed	to calculate sample size,
Puberty	3 072 hove 8-18 vrs	was about 19 µg/L.	puberty and the	but sample sizes in this
	2.903 girls, 8-18 yrs		delayed puberty had	study were enough for sufficient precision
	-,000 8		narrow Cls	
ADHD	Stein 2011, C8	PFHxS mean serum level		
	10,546; aged 5-18	was 5.2 µg/L. 4 th vs 1 st		
	yrs.	quartile,	Prevalence:	764/24224
		0K=1.5	AUHU UX: 12.4%	764/stratum
Asthma	Stein 2016, NHANES	PFOA mean serum level =	Prevalence = 11%	2,400/stratum
	640; 12-19 yrs	3.6 μg/L.		
		OR=1.2		
Atopic	Wang 2011 (Taiwan)	PFOS mean serum	Prevalence=10.7%	220/stratum
dermatitis	244; infants, 2 yrs	level=5.5 μg/L., 4''' quartile OR=2 19		
Obesity	Karlsen 2017	PFOA mean serum	Prevalence=17%	250/stratum
	(Faroes)	level=2.22 μg/L. OR=1.88		

1 Note: Observed effect sizes focused on the results for serum levels of PFOS and/or PFHxS.

¹ eGFR –estimated glomerular filtration rate, TT4 – total thyroxine; IGF-1 – insulin-like growth factor 1; ADHD – attention-deficit
 and hyperactivity disorder.

4

5 3.3.2 Adults

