 OR=3.05) was consistent for PFOA serum levels considerably lower than those in the C8 study. For more

- 1 modest effect sizes (e.g., ORs < 2.75), a total sample size of 6,000 would not be adequate to evaluate
- 2 associations with ulcerative colitis.
- 3 In addition, several epidemiological studies of adults exposed to PFAS that reported robust statistical
- 4 associations with these health outcomes had smaller sample sizes than the one proposed for the Multi-
- 5 site Study, e.g., NHANES studies (Nelson 2010, Wen 2013), a C8 longitudinal study (Fitz-Simon 2013), a C8
- 6 immune study (Looker 2014), and studies in China (Fu 2014) and Korea (Ji 2012).
- 7 In summary, a total sample size of ≥6,000 in multi-site study should be sufficient to evaluate a broad range
- 8 of biomarkers and outcomes such as lipids (and hypercholesterolemia), uric acid (and hyperuricemia),
- 9 cardiovascular disease, osteoarthritis, immune biomarkers and biomarkers for fatty liver disease. It also
- 10 may be sufficient to evaluate thyroid disease, thyroid function and liver function.
- 11 **Table 2.** Sample size estimations for selected health-related endpoints in Adult Study.

Health-related Endpoint	Relevant Study	Observed Effect Size	Assumptions	Sample Size/Stratum α error = .05 β error = .20
Total Cholesterol (mg/dL)	Steenland 2009, C8 46,294 aged ≥18 yrs	PFOS, mean serum level = 19.6 μg/L, 10 th vs 1 st decile:+11 mg/dL	SD=41.9	228/stratum
High cholesterol		4 th vs 1 st quartile, OR=1.51	Prevalence=15%	660/stratum
High Cholesterol	Fisher 2013, Canada	PFHxS, mean serum level = 2.2 μ g/L, 4 th vs 1 st quartile, OR=1.57	Prevalence=44%	290/stratum
Cardiovascular disease	Shankar 2012, NHANES 1,216 aged ≥40 years	PFOA mean serum level = 4.2 μ g/L, 4 th vs 1 st quartile: OR=2.01	Prevalence = 13%	250/stratum
Uric Acid	Steenland 2010, C8 53,458 aged ≥20 yrs	PFOS mean serum level = 20.2 μg/L, 10 th vs 1 st decile: +0.22 mg/dL	SD=1.55	780/stratum
		Hyperuricemia, 5 th vs 1 st quintile: OR=1.26	Prevalence:24%	1,525/stratum
Uric Acid	Shankar 2011, NHANES 3,883 aged ≥20 yrs	PFOA mean serum level = 3.5 μg/L, 4 th vs 1 st quartile: +0.44 mg/dL	SD = 2.5	507/stratum
		Hyperuricemia, 4 th vs 1 st quartile: OR=1.97	Prevalence: 19.2%	200/stratum
		PFOS mean serum level = 17.9 μg/L		550/stratum

		Hyperuricemia, 4 th vs 1 st quartile: OR=1.5		

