Liver function Elevated ALT	Gallo 2012, C8 46,452 aged ≥18 yrs	PFOA and PFOS mean serum levels were 28 μg/L and 20.3 μg/L, respectively. PFOA: OR=1.54 PFOS: OR=1.25	Prevalence = 11.2%	725/stratum 2,917/stratum
Liver function ALT (μΙU/mL)	Gallo 2012, C8 46,452 aged ≥18 yrs	The top quintile of serum PFOS in the Pease population was 15 μ g/L. This would approximately correspond to a mean difference in ALT of +1.8 μ IU/mL	SD=1.47	1,958/stratum
Liver function Elevated ALT	Gleason 2015, NHANES 4,333 aged ≥12 yrs	PFHxS mean serum level = 1.8 μg/L. 4 th vs 1 st quartile: OR=1.37	Assumed similar prevalence as in the C8 study	1,570/stratum
Thyroid disease	Melzer 2010, NHANES 1,900 men, aged ≥20 yrs 2,066 women, aged ≥20 yrs	PFOA, mean serum level=3.5 μg/L, 4 th vs 1 st quartile: Thyroid disease ever: Women, OR=1.64 Men, OR=1.58 Thyroid disease with current meds Women OR=1.86	Prevalences: 16.18% 3.06%	410/stratum 2,035/stratum
		Men, OR=1.89	1.88%	1,575/stratum
Subclinical hypothyroidism	Wen 2013, NHANES 672 males aged ≥20 yrs 509 females aged ≥20 yrs	PFHxS mean serum level averaged about 2 μg/L. Unit increase in Ln(PFHxS): Women, OR=3.10 Men, OR=1.57	Prevalences: 1.6% 2.2%	475/stratum 2,918/stratum
Osto o utbuitio	Jan es 2011 - C0	00-142	Drevelopes 7 C0/	1 500 / atmatume
Osteoartmitis	49,432 aged >20 vrs	0n-1.42	FIEVAIENCE=7.0%	1,580/stratum
Osteoarthritis	Uhl 2013, NHANES 4,102 aged 20-84	PFOA mean serum level = 5.4 μ g/L , 4 th vs 1 st quartile: OR=1.55 PFOS mean serum level = 24.6 μ g/L , 4 th vs 1 st quartile: OR=1.77	Assumed similar prevalence as in the C8 study	978/stratum 550/stratum
		$\mu_{\text{B}/\text{L}}, 4^{}$ vs 1 quartile: OK=1.77		
Ulcerative colitis	Steenland 2013, C8 28,541 community and 3,713 worker cohorts	OR=3.05	Prevalence=0.5%	1,480/stratum

1 For rare health outcomes such ulcerative colitis, other autoimmune diseases, or cancer the sample size of

2 6,000 adults is too small to detect reasonably expected increases in the ORs.

3 It should be noted that the number of PFAS epidemiological studies available for each of the outcomes is

4 limited, and the actual differences in clinical and research parameters may be quite different in the Multi-

site study than have been observed in the PFAS literature. Sample size estimates provide guidance and
 may be useful for planning purposes but should be interpreted with caution, especially given the limited
 nature of the PFAS literature.

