 the source via ground water, then the recipient should seek information on the extent of the
 contamination plume from the state environmental agency, EPA, and/or the industrial facility.

If the contaminated drinking water is from a municipal system, then the characteristics of the distribution system will be obtained from the water purveyor. If supply wells are used, then the recipient will request historical and current information on these wells including monthly or daily production logs and dates of operation. If a surface water source is used or if water is purchased from another purveyor, then the recipient will request information about this source.

10 The recipient will also request the results of all relevant PFAS sampling: in the surface water near the 11 drinking water intakes, in the distribution system, in the supply wells and nearby monitoring wells, in 12 purchased water from other water purveyors, and in the private wells in the study area.

13

14 **3.10 Statistical Analyses**

15 ATSDR staff will perform statistical analyses with the participation of the recipients using SAS, R and STATA 16 on the combined multi-site study dataset. ATSDR staff may also use SPSS for data management. ATSDR 17 staff will calculate descriptive statistics (including means, geometric means, medians, standard deviations, 18 and percentiles) to identify the presence and distribution of PFAS and effect biomarker analytes. Statistical 19 methods will include multiple linear regression of continuous (untransformed and natural log transformed) effect biomarkers on continuous (untransformed and natural log transformed) PFAS serum 20 21 levels and categorized PFAS serum levels, and logistic regression of categorized effect biomarkers (e.g., 22 hypercholesterolemia) or disease prevalence on continuous (untransformed and natural log transformed) 23 and categorical PFAS serum levels. ATSDR staff will use restricted cubic spline methods (or generalized 24 additive models using cubic regression splines) for linear and logistic regression to obtain flexible, 25 smoothed exposure-response curves. To identify risk factors that may act as confounders for a particular health outcome, the analysis will implement a "10% change in the estimate" rule (Maldonado 1993). 26

Primary analyses will focus on estimated cumulative PFAS serum levels. Supplemental analyses will
evaluate PFAS serum levels in the blood specimens obtained in the study as well as estimated maximum

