Attachment 3b. Adult Study

The following provides information on the parameters and sample size calculation used in Table 2 for the adult study.

Sample size calculations were conducted with type 1 (" α error") set at .05 and type 2 error (" β error) set at .20. It was considered important that a study have a total sample size so that exposures could be categorized into tertiles (i.e., reference level, medium level, and high level) or preferably into quartiles (i.e., reference level, low, medium and high).

Studies were selected that were considered the most representative of U.S. populations exposed via drinking water to PFOA, PFOS and/or PFHxS as a result of the migration of these PFAS chemicals into ground water or surface water sources from the use of aqueous film forming foam (AFFF). The PFOS, PFOA and PFHxS results in the NHANES studies were used in many of the sample size calculations. For those outcomes not included in NHANES studies, the C8 studies were used. Where applicable studies from Taiwan or other major industrialized countries were also used.

Example:

Liver Function – Adults

In the C8 study (Darrow 2016), the mean alanine aminotransferase (ALT) level was 26 IU/L and the standard deviation was 19. The linear regression coefficient for the natural log ALT in the fifth quintile level of cumulative natural log PFOA was 0.058. Assuming that the reference group had an ALT level equal to the mean, the natural log of the mean ALT would be 3.26. Therefore the natural log of ALT for the fifth quintile cumulative log PFOA would be 3.32. Exponentiating 3.32 equals 27.6. The mean difference in the untransformed ALT is then 1.6.

Assuming a 95% CI and 80% power, the sample size = 2,214/group.

Thyroid Function – Adults (not included in Table 2)

In a study done by Shrestha 2015, the sample size was 87 adults aged 55-74. Mean and SD for TSH was 2.58 μ IU/mL and 1.47, respectively. The linear regression of the natural log TSH resulted in a coefficient for the natural log PFOS of 0.129. Using a PFOS level of 15 ng/mL, the natural log of 15 is 2.71; multiplied by 0.129 equals 0.35. The reference level TSH was assumed to be the median TSH of 2.15 μ IU/mL. The natural log of 2.15 is 0.77; adding 0.35 equals 1.12. Exponentiating 1.12 equals 3.06. The mean difference is then 3.06 – 2.15 = 0.91. The standard deviation of 1.47 was used for each group.

Assuming a 95% CI and 80% power, the sample size = 41/group.

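### Adult liver function: the only size based on cumulative exposure, the primary metric (ALT, 2,214 per group), is missing from Table 2 and contradicts the stated total of 3,000 to 4,000

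*Protocol*

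**What the plan says.** Protocol section 3.10: "Primary analyses will focus on estimated cumulative PFAS serum levels". Serum measured in the study's own samples, together with modelled peak and mean levels, is left to supplemental work.

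Most rows of Tables 1 and 2 give a mean PFAS serum level with a quartile, quintile or decile contrast. A few, such as ulcerative colitis and one osteoarthritis row, state no metric. No row is labelled as a cumulative-exposure effect. The note under Table 1 reads: "Note: Observed effect sizes focused on the results for serum levels of PFOS and/or PFHxS". Section 3.3 says the totals should allow categories of serum or of cumulative serum, but does not say which of the two the effect sizes describe.

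Attachment 3b introduces itself as the source of the parameters and calculations behind Table 2. Its liver example is based on cumulative exposure: "The linear regression coefficient for the natural log ALT in the fifth quintile level of cumulative natural log PFOA was 0.058". From a mean ALT of 26 and an SD of 19 it concludes: "The mean difference in the untransformed ALT is then 1.6", and gives 2,214 per group. The thyroid example that follows is marked as not included in Table 2. The liver example carries no such mark, yet 2,214 does not appear in Table 2.

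The continuous ALT row that does appear in Table 2 starts from a serum level ("The top quintile of serum PFOS in the Pease population was 15" µg/L), takes a difference of 1.8 and an SD of 1.47, and prints 1,958 per stratum.

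Section 3.3.2 puts the total needed for liver function or osteoarthritis at 3,000 to 4,000. Its summary says 6,000 adults "may be sufficient to evaluate thyroid disease, thyroid function and liver function". Section 1.1.3 says more generally that power should be sufficient for effects of the size seen in other well-designed studies.

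**The concern.** A reader of section 3.3 will take its sizes as support for the primary analysis. For ALT the protocol contains a calculation on the primary type of exposure, and that calculation gives a much larger requirement than the liver total quoted in the text. Leaving it out of Table 2 hides the conflict.

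A reader relying on 3,000 to 4,000 would think that 6,000 adults leave a comfortable margin for liver function. On the Attachment 3b figures they fall short of 80% power in both quartiles and tertiles. The row shown in its place cannot be reproduced from its own inputs.

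**Working it through.** **Inputs.** From Attachment 3b: difference 1.6, SD 19 in both groups, two-sided alpha 0.05, 80% power, equal groups. From section 3.3.2: 6,000 adults, and 3,000 to 4,000 for liver function. Attachment 3b prefers quartiles, with tertiles as the alternative.

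**Reproducing the stated size.** n = 2 x SD² x (1.96 + 0.8416)² / difference² = 2 x 361 x 7.849 / 2.56 = 2,214 per group. This matches Attachment 3b.

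**Totals for 80% power.** Quartiles: 4 x 2,214 = 8,856. Tertiles: 3 x 2,214 = 6,642.

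**Power at the available sizes.** Power = Phi(1.6 / (19 x sqrt(2/n)) - 1.96), lowest against highest stratum:

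| Total adults | Split | n per stratum | Power |
|---|---|---|---|
| 6,000 | tertiles | 2,000 | 75.9% |
| 6,000 | quartiles | 1,500 | 63.5% |
| 6,000 | quintiles | 1,200 | 54.1% |
| 4,000 | quartiles | 1,000 | 46.9% |
| 3,000 | quartiles | 750 | 37.1% |

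At 1,500 per stratum, the difference detectable with 80% power is 1.94.

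**Sensitivity to rounding.** The unrounded difference is 26 x (exp(0.058) - 1) = 1.55. It needs 2,351 per group and gives 60.9% in quartiles and 73.4% in tertiles.

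**The serum-based ALT row.** With the printed inputs, 2 x 1.47² x 7.849 / 1.8² = 10.5, so 11 per stratum against 1,958 printed. With SD 19 the same difference needs 1,750. The printed 1,958 implies an SD of about 20.1. In Attachment 3b, 1.47 is the SD of TSH in µIU/mL, and the Table 2 ALT row is also labelled µIU/mL, so the SD looks carried over from the wrong analyte. Taken as printed, 4 x 1,958 = 7,832 exceeds 6,000, while 3 x 1,958 = 5,874 does not.

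**All ALT rows as printed, over quartiles:**

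| Row | n per stratum | x 4 |
|---|---|---|
| Elevated ALT, PFOA, OR 1.54 | 725 | 2,900 |
| Elevated ALT, PFHxS, OR 1.37 | 1,570 | 6,280 |
| Continuous ALT, PFOS serum | 1,958 | 7,832 |
| Continuous ALT, cumulative PFOA (Attachment 3b only) | 2,214 | 8,856 |
| Elevated ALT, PFOS, OR 1.25 | 2,917 | 11,668 |

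Only the first row is compatible with a liver total of 3,000 to 4,000.

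**The case against.** **The protocol already hedges.** It keeps liver function out of the list for which 6,000 should be enough, asks that sample sizes be read with caution, and says it will interpret effect sizes and confidence intervals rather than significance alone. This stands and limits the harm. It does not explain the 3,000 to 4,000 figure or the missing row.

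**The stratum comparison is not the whole analysis.** Section 3.10 also plans regression on continuous exposure and on log-transformed outcomes, and 0.058 is itself a log-ALT coefficient. A reader might infer that 64% is the power of the primary analysis. The documents do not support that. The SD of log ALT is not given. If it were 0.50 to 0.65 (an assumption), power for 0.058 at 1,500 per stratum would be about 89% to 69%. Power for continuous exposure cannot be derived from the protocol.

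**The exposure metric is not isolated.** A reader might infer from 1.6 against 1.8 that modelled cumulative exposure shrinks the ALT effect. The 1.6 is for cumulative PFOA in one C8 study and the 1.8 for serum PFOS in another, so chemical, study and contrast all differ. Much of the shortfall exists without any change of metric: a difference of 1.8 at 1,500 per stratum gives 74% power with SD 19 and 69% with SD 20.1.

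**Relabelling every size as supplemental would go too far.** Section 3.3 explicitly allows for categories of cumulative serum, and some rows state no metric.

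**eGFR.** Section 2.5.1.2 reports that "modeled PFOA concentrations had no relation to eGFR" although measured PFOA was associated. A reader might infer that the child eGFR size (275 per stratum) has no bearing on the primary analysis. That does not follow. A difference of 6.6 with SD 27.6 needs 275 per stratum whichever metric defines the strata. The 2,000 children give 500 per quartile and about 97% power. An absent modelled association is not a lack of power.

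**Conclusion.** The point holds for adult ALT and for the wording of section 3.3. The effect sizes rest largely on serum-level studies and the text does not say so. The one cumulative-exposure calculation is left out of Table 2, and it contradicts the 3,000 to 4,000 stated for liver function, which would give 37% to 47% power in quartiles. The planned 6,000 adults give about 64% in quartiles or 76% in tertiles, against the 80% used for planning. Separately, the serum-based ALT row is wrong as printed.

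These power figures assume a two-group comparison of extreme strata on untransformed ALT, SD 19, equal strata, and the protocol's rounded difference of 1.6. That difference is a fifth-quintile effect for one chemical in one population. If the trend is monotone, a quartile contrast would be somewhat smaller and power a little lower. The finding says nothing about the adequacy of 6,000 for other outcomes and does not question the choice of primary exposure.

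**What to change.** 1. In section 3.3, state that the effect sizes in Tables 1 and 2 rest largely on studies of serum levels, while the primary exposure is modelled cumulative serum.
2. Add the Attachment 3b calculation to Table 2 as a row: ALT, cumulative PFOA, difference 1.6, SD 19, 2,214 per stratum.
3. Correct the serum-based ALT row: give the SD actually used, check the unit, and recompute the size.
4. In section 3.3.2, replace 3,000 to 4,000 for liver function with the totals the protocol's own rows imply. Over quartiles these are 2,900 to 11,668 as printed, with 8,856 for the cumulative row (6,642 over tertiles).
5. State that for the cumulative ALT effect 6,000 adults give about 64% power in quartiles and 76% in tertiles for the stratum comparison, and that power for continuous-exposure or log-ALT regression has not been calculated.
6. Leave the eGFR sufficiency statement in place, noting only that its 6.6 comes from measured PFOA.

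The cost is a few sentences, one new table row and one corrected row. Enrolment, design and primary exposure do not change. The stated position on liver function becomes less favourable.
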